## 4 PATIENT SELECTION

### 4.1 Inclusion Criteria

A patient must meet all of the following inclusion criteria to be eligible for this study.

4.1.1 Pathologically-proven diagnosis of a solid tumor malignancy

4.1.2 One of the following criteria must be met:

- 4.1.2.1 Clinical or radiographic evidence of disease control (defined as best response of SD or PR or combination of both for  $\geq 16$  weeks) without evidence of CR or progression

**OR**

- 4.1.2.2 Clinical or radiographic evidence of disease progression during treatment with PD-1 or PD-L1 inhibiting therapy, following previous tumor response (CR, PR, or SD for  $\geq 16$  weeks) to PD-1 or PD-L1 inhibiting therapy,

**and**, for patients who discontinued PD-1 or PD-L1 inhibiting therapy during response to therapy, disease progression must have occurred following at least 8 weeks of re-treatment with PD-1 or PD-L1 inhibiting therapy

Note: Both the treating medical oncologist and radiation oncologist must be in agreement with determination of disease progression.

4.1.3 Administration of a PD-1 or PD-L1 inhibitor within 60 days prior to study registration

4.1.4 Determination by the treating radiation oncologist that the patient is a candidate for SRT (ie, radiation therapy with a stereotactic setup)

Note: All brain metastases will receive SRT.

4.1.5 The total number of tumors requiring SRT must be  $\leq 5$

Note: Regardless of the number of brain metastases that will be treated with SRT, the brain metastases will be considered to be one tumor.

- 4.1.6 Measurable disease by RECIST v1.1 that will not undergo SRT and that is amenable to monitoring

Note: As noted in Section [4.1.6](#), all brain metastases will receive SRT. Therefore, a patient with brain metastases that will be treated with SRT must also have extracranial disease that will not undergo SRT and that is amenable to monitoring (also see Section [1.6](#) and Section [13.2](#)).

- 4.1.7 Determination by the treating medical oncologist that the patient is a candidate to continue the PD-1 or PD-L1 inhibiting therapy that had previously provided disease control

- 4.1.8 Age  $\geq$  18 years

- 4.1.9 Karnofsky Performance Status score of  $\geq$  60 % (see [Appendix 1](#) for criteria)

- 4.1.10 A woman of childbearing potential (WCBP), defined as a woman who is < 60 years of age and has not had a hysterectomy, must have a documented negative serum pregnancy test within 14 days prior to initiating study treatment

- 4.1.11 Ability to understand and willingness to sign the consent form

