## **3 STUDY DESIGN**

### **3.1 General Description**

This study is a phase 2 single-arm clinical trial of SRT delivered concurrently with PD-1 or PD-L1 inhibiting therapy to determine if standard SRT potentiates the abscopal effect of PD-1 or PD-L1 inhibiting therapy in patients with an advanced solid tumor who previously achieved disease control from PD-1 or PD-L1 inhibiting therapy but are no longer continuing to improve. Eligible patients must have 1 to 5 metastatic, recurrent, or primary tumors that are clinically appropriate to receive SRT and at least one additional tumor that is measureable but will not be treated using SRT.

SRT will be delivered over 1 to 2 weeks. Patients will continue to receive the same FDA-approved PD-1 or PD-L1 inhibitor that they had been receiving previously until 52 weeks following completion of SRT.

Correlative blood samples will be collected at baseline, prior to the second SRT fraction, after the last SRT fraction (on the same day), and at 8, 24, and 52 weeks after the last SRT fraction. These samples will be used to determine the mechanistic immunologic effects of therapy.

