### 3.4 Secondary Endpoints

- 3.4.1 Proportion of patients alive and free from progression (ie, CR, PR, or SD) per unidimensional irRC and, if brain metastases are present, per iRANO criteria at 24 weeks following SRT
- 3.4.2 Proportion of patients with treatment response (ie, CR, PR, or SD) at irradiated tumor sites at 24 weeks following SRT (refer to Section [10.1](#) for response criteria)
- 3.4.3 Proportion of patients with treatment response (ie, CR, PR, or SD) at non-irradiated tumor sites at 24 weeks following SRT (refer to Section [10.1](#) for response criteria)
- 3.4.4 Proportion of patients who are alive at 2 years after completion of SRT
- 3.4.5 Adverse events including the following:
  - All SRT-related and immunotherapy-related  $\geq$  grade 3 adverse events per the most current National Cancer Institute (NCI) Common Terminology Criteria for Adverse Events Version 5.0 (CTCAE v5.0) occurring from initiation of SRT until 8 weeks after the last SRT fraction
  - All immunotherapy-related adverse events (AEs) occurring from 8 weeks post-SRT until 2 years post-SRT requiring discontinuation of PD-1 or PD-L1 inhibiting therapy and concurrent initiation of immunosuppressive agents such as steroids as described in Section [8.5.2](#).

- 3.4.6 Radiobiological signature as described in Section [1.9.3](#) using blood samples collected prior to SRT (baseline), prior to the 2nd SRT fraction, immediately following completion of SRT (on same day); and at 8, 24, and 52 weeks following completion of SRT

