### 6.3.2 Dose Specifications

- Treatment will be planned to deliver a total of 18 to 60 Gy to the planning target volume (PTV) in up to 10 fractions over 1 to 2 weeks.
- The dose per fraction is to be prescribed so that at least 95% of the PTV receives the prescription dose.

Note: Metastases in different locations may be treated to different doses in the same patient.

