#### 6.3.4 Treatment Planning

- Planning Constraints

Planning constraints are provided in this section for both the PTV as well as critical normal structures to be spared. Acceptable treatment plans will be established from a DVH-based analysis of the volumetric dose to both the PTV and critical normal structures to ensure that minimally acceptable constraints for each volume of interest have been met.

- Planning Techniques

Planning techniques may differ for each lesion to be treated provided that the tumor motion is properly accounted for with each technique when the target or targets are in or near the thorax region.

- Planning SRT Near Prior Radiotherapy Volumes

The toxicity of delivering SRT to multiple metastases in close proximity to prior conventionally-fractionated external beam RT volumes is not known. Every effort should be made to limit the dose to organs at risk that have previously received radiation.

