
A. Assessment of Medical History will include, if known, baseline tumor characteristics: PD-L1 expression and Microsatellite Instability-High (MSI-H) status
 
B. Baseline imaging should be contrast-enhanced and include the following:
 

CT, PET-CT, and/or MRI of all suspected sites of disease within 28 days prior to study registration; for patients with a documented CT and/or MRI contrast allergy, the CT and/or MRI may be performed without contrast.

Brain (CT or MRI) within 1 year prior to study registration to screen for brain metastasis. In patients with known brain metastasis, brain imaging must be performed within 28 days prior to study registration.

 
Note: The imaging used at baseline should be used at each subsequent imaging time point.
 
C. Disease assessment by imaging and/or clinical examination. For patients with brain metastasis receiving SRS, disease assessment includes documentation of neurologic status and dosing history of steroids used for CNS edema management.
 
D. To determine if the patient is a candidate for SRT and if there is at least one lesion that will not receive SRT.
 
E. Consultation or, if the patient's treating medical oncologist is a VCU MCC sub-investigator, documentation that the patient is a candidate to continue PD-1 or PD-L1 inhibiting therapy.
 
F. Refer to Section 6.5.3.
 
G. Assessment to determine if AEs related to previous therapy have resolved or stabilized.
 
H. Chemistry includes the following panels and tests: basic metabolic panel (sodium, potassium, carbonate, chloride, glucose, calcium, BUN, and creatinine); hepatic panel (ALT, AST, ALP, total bilirubin, direct bilirubin, albumin, and total protein).
 
I. Only required for WCBP (see Section 4.1.12); if required, perform within 14 days prior to study registration. If SRT cannot begin within 14 days of a negative pregnancy test, the pregnancy test must be repeated prior to initiation of SRT. Serum or urine qualitative pregnancy test is acceptable.
	

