### 13.4 Statistical Analysis of Secondary Objectives

Patients' demographics, AEs and SAEs, disease status, treatment status, clinical response, etc will be listed and summary descriptive statistics will be calculated. Rate of higher grade AEs will be reported at each follow-up visit.

Time to death, time to progression at the irradiated site, and time to progression at a non-irradiated site will be summarized using the Kaplan Meier survival curve. Overall survival probabilities will be estimated with 95% confidence intervals at each follow-up time point during the 2-year follow-up. Analysis of the secondary objectives will include all evaluable patients; however, a subset analysis of evaluable patients who only receive SRT to brain metastases will also be performed.

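### Lesions analysed as non-irradiated are defined only as not targeted by SRT, so a direct radiation effect can be scored as abscopal control in endpoint 3.4.3 and the related time-to-progression curve

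*Combined protocol and SAP*

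**What the plan says.** Section 3.1 gives the purpose of the trial as "to determine if standard SRT potentiates the abscopal effect of PD-1 or PD-L1 inhibiting therapy". It asks for 1 to 5 tumors suitable for SRT and "at least one additional tumor that is measureable but will not be treated using SRT". Inclusion criterion 4.1.6 repeats the condition: "Measurable disease by RECIST v1.1 that will not undergo SRT and that is amenable to monitoring". Section 6.1 has treated and monitored tumors identified before SRT starts. The screening check in Table 4, note D, is "To determine if the patient is a candidate for SRT and if there is at least one lesion that will not receive SRT".

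The analysis sections use a different term. Endpoint 3.4.3 is "Proportion of patients with treatment response (ie, CR, PR, or SD) at non-irradiated tumor sites at 24 weeks following SRT", and Section 13.4 adds that "time to progression at a non-irradiated site will be summarized using the Kaplan Meier survival curve".

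On dose, Section 6.3.2 allows planned totals of 18 to 60 Gy in up to 10 fractions. Section 6.3.8 limits dose to critical structures and organs at risk. On earlier radiotherapy, Section 6.3.4 warns: "The toxicity of delivering SRT to multiple metastases in close proximity to prior conventionally-fractionated external beam RT volumes is not known". Exclusion 4.2.1 bars other anti-cancer therapy between the response to PD-1/PD-L1 therapy and enrollment, and Section 6.5.1 names RT as cancer treatment.

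**The concern.** Not targeted and not irradiated are different properties. A lesion beside a target receives part of the dose planned for its neighbour, and with up to five targets it may receive dose from more than one plan. A lesion irradiated before immunotherapy began to work may be held in check by that treatment. Either kind of lesion can enter 3.4.3 and the time-to-progression curve as evidence of an effect at a distance.

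These two analyses are the only ones in the plan that separate untargeted from targeted disease, so they carry the abscopal question. A direct antitumor effect pushes both towards apparent control. The trial has one arm, so nothing offsets the bias. Endpoint 3.4.3 is also easy to satisfy: a dose that merely stops a lesion growing for 24 weeks yields SD, which counts as response.

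**Working it through.** **1. How the lesion is defined and how it is analysed**

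| Place | Basis | Dose or distance condition |
|---|---|---|
| 3.1, 4.1.6, 6.1 | not an SRT target | none |
| Table 4, note D | will not receive SRT | none |
| 13.5.2 | tumor not treated by SRT | none |
| 2.2.3, 3.4.3, 13.4 | non-irradiated site | none; term not defined |

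No section links the two terms. Section 6.3 limits captured radiotherapy data to what the eCRFs require, and no section asks for the dose to untargeted lesions.

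**2. Which radiation can reach a monitored lesion**

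- Radiotherapy before the PD-1/PD-L1 response: not excluded, and no lesion-level record is stated.
- Radiotherapy between that response and enrollment: excluded by 4.2.1, read with 6.5.1.
- Non-protocol radiotherapy once study therapy has started: barred by 6.5.1 until progression.
- Protocol SRT to neighbouring targets: no limit for untargeted tumors. Section 6.3.10 foresees several lesions in one anatomical site. Under Section 6.3.7 the ITV covers likely microscopic disease and the PTV adds 1 to 5 mm.

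Two routes remain open: the first and the last.

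**3. The plan's own figure**

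Inputs from Sections 13.2 and 13.3: null rate 10%, target rate 25%, 14 patients in stage 1, continue with at least 2 successes, 42 in total, positive with at least 8. (Section 3.2 gives different stage sizes; that is a separate matter.)

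P(positive) = sum over x = 2 to 14 of P(X1 = x) × P(X2 ≥ 8 − x), with X1 ~ Bin(14, p) and X2 ~ Bin(28, p).

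- p = 0.10: 0.0464, within the stated 5%.
- p = 0.25: 0.804, matching the stated 80%.

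The design reproduces. It tests patient-level disease control (Sections 3.3 and 13.1), which does not depend on labelling lesions as irradiated or not. Mislabelling cannot change it.

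**4. Possible size in 3.4.3**

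Let k be the number of patients whose 3.4.3 result depends on exposed lesions, u the share of them who would fail without the dose, and d the chance that the dose turns a failure into a success. Then inflation = (k/42) × u × d. The documents give none of k, u or d; the 42 assumes the evaluable number in Section 13.3.

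| k (assumed) | u = d = 1 | u = 1, d = 0.5 |
|---|---|---|
| 1 | 1/42 = 2.4 points | 1.2 points |
| 3 | 3/42 = 7.1 points | 3.6 points |
| 5 | 5/42 = 11.9 points | 6.0 points |

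The middle column is the ceiling for each k.

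**The case against.** The best case against the point has five parts.

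- **The affected analyses decide nothing.** Endpoint 3.4.3 and the curve are secondary and descriptive, with no null rate or decision rule. In a single arm with SD counted as response, 3.4.3 could not isolate an abscopal effect even with perfect labelling. This stands and limits the weight of the point. It does not justify adding an avoidable bias to the analysis closest to the stated aim.
- **Earlier radiotherapy is largely dealt with.** Exclusion 4.2.1 removes radiotherapy given after the response, and baseline imaging within 28 days of registration absorbs older shrinkage. This stands for later radiotherapy and for shrinkage. It does not cover a lesion irradiated before the response that simply stays stable. RECIST v1.1 measurability may narrow this further, but the documents cite that text without reproducing it.
- **Dose may be recorded anyway.** The eCRFs are not in the documents, so one can say only that no requirement is stated. The plans will exist, so a later look is possible. A cut-off chosen after the results are known would carry little weight.
- **Equal totals are not equal effect.** A reader might note that 18/60 = 30% and infer that a lesion at 30% of a 60 Gy plan gets a full protocol treatment. In 10 fractions that is 0.30 × 6 = 1.8 Gy per fraction. The documents give no dose fall-off distances, so the inference fails.
- **Some surroundings are already target.** The ITV takes in nearby microscopic disease. That is true, but the same wider field brings dose closer to untargeted neighbours.

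**Conclusion.** The point holds for secondary endpoint 3.4.3 and for time to progression at a non-irradiated site. Both can count direct radiation effect as abscopal control, and the expected bias is favourable. The route is an untargeted lesion near SRT targets, or one irradiated before the PD-1/PD-L1 response.

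The size cannot be estimated from the documents. The range of 2 to 12 points assumes 1 to 5 affected patients among 42, all of whom would otherwise have failed and all rescued by the dose. It is a ceiling for those counts. A patient with another untargeted lesion that progresses would not be rescued, and one who would have been stable anyway adds nothing.

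Two stronger readings should be resisted:

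- A reader might infer that the primary result or its error rate is inflated. It is not: the primary endpoint is patient-level, and the two-stage rule of Section 13.3 does not apply to 3.4.3.
- A reader might infer that any earlier radiotherapy to the monitored lesion goes unchecked. Exclusion 4.2.1, read with 6.5.1, rules out radiotherapy between response and enrollment.

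This is a cheap improvement to the trial's answer on its abscopal question, not a defect in its primary design.

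**What to change.** Leave eligibility unchanged. A dose test in 4.1.6 could not be applied, because lesion dose is known only after planning and SRT may start up to 4 weeks after registration.

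- **Section 6.1 and the eCRF:** for each monitored lesion, record the planned maximum dose summed over all SRT plans, where the planning CT covers the lesion, and any prior radiotherapy to it.
- **Section 13.4:** have the investigators and the physicist prespecify the analysis criterion for non-irradiated before any response data are analysed. That means before the stage 1 summary, which under Section 13.3 already includes the secondary endpoints.
- **Section 13.4, reporting:** give 3.4.3 and the non-irradiated time-to-progression curve twice, for all untargeted lesions and excluding exposed lesions. State how many lesions and patients leave the restricted set.

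This changes no treatment, dose or schedule. The cost is some contouring and data abstraction from existing plans and radiotherapy history, a few eCRF fields and a short analysis paragraph. The downside is slightly fewer lesions in the restricted analysis; a patient with no unexposed monitored lesion would drop out of it but stay in the all-lesion result.

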## 4.2 Exclusion Criteria

- 4.2.1 Other anti-cancer therapy administered between the time of tumor response to PD-1 or PD-L1 therapy and time of study enrollment

Note: Patients treated with a combination of PD-1 or PD-L1 inhibiting therapy and other immunotherapy are eligible; patients taking hormonal anti-cancer therapies or steroids for central nervous system (CNS) edema management that, in the opinion of the investigator, are appropriate to continue are eligible.

- 4.2.2 Any prior PD-1/PD-L1 therapy-related AE that, in the opinion of the investigator, warrants exclusion from participation in this trial

- 4.2.3 Administration of any investigational agent within 4 weeks prior to initiating study treatment

- 4.2.4 Known active hepatitis B or C

- 4.2.5 Pregnancy or breastfeeding

- 4.2.6 Medical, psychological, or social condition that, in the opinion of the investigator, may increase the patient's risk or limit the patient's adherence with study requirements

## 5 STUDY ENTRY AND WITHDRAWAL PROCEDURES

### 5.1 Study Entry Procedures

#### 5.1.1 Required Pre-Registration Screening Tests and Procedures

Refer to the study calendar in Section [12](#) for the screening tests and procedures that are required prior to registration and for the timing of these events relative to the start of treatment.

#### 5.1.2 Registration Process

Study registration will be performed by the study team [REDACTED]. The following documents are required for study registration:

- Completed, signed, and dated eligibility checklist
- Signed and dated consent form

The registrar will complete the registration process by assigning a study ID number. Study treatment may not begin until the Confirmation of Registration has been received and a study ID number has been assigned.

The study team submitting registration documents to the registrar will enter the patient's initial enrollment data (eg, demographics, consent, eligibility, on study) into the OnCore database within 24 hours following study registration (before the first SRT fraction).

### 5.2 Study Withdrawal

A patient may decide to withdraw from study participation at any time. Patients must be removed from the study when any of the following occurs:

- The patient has withdrawn consent for study treatment and study procedures
- If, in the investigator's opinion, continuation of the study requirements would be harmful to the patient's well-being
- The patient is lost to follow-up
- The sponsor has terminated the study

The reason for and date associated with study withdrawal or removal from the study must be documented in source documents and in the OnCore database.

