## 6.6 Duration of Therapy

Study treatment will be administered as described in Sections [6.3](#) and [6.4](#) unless one of the following occurs (also see study withdrawal criteria in Section [5.2](#)):

- AE that requires discontinuation of study treatment
- Pregnancy
- Determination by the investigator that discontinuation is in the patient's best medical interest
- Patient decision to discontinue study treatment
- Withdrawal of study sponsor support

The reason for discontinuation of study treatment must be documented in the source documents and in the OnCore database.

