#### 6.7.2 Follow-up for Treatment Response and Survival

Patients who remain on study will be assessed according to the study calendar ([Table 5](#)) through 2 years after completion of SRT.

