- P. SRT must be administered by VCU Radiation Oncology and must begin within 4 weeks following study registration; refer to Section [6.3](#) for additional SRT requirements and instructions.
- Q. If one dose of the PD-1 or PD-L1 inhibitor needs to be given after study registration (before the first SRT fraction), the pre-SRT dose (if given) must be timed so that the next dose is given on the same day as the last SRT fraction.
- R. At the discretion of the treating medical oncologist, the PD-1 or PD-L1 inhibitor may continue to be administered after 52 weeks following completion of SRT if there has not been disease progression following SRT.
- S. For patients with post-SRT disease progression, follow-up can be limited to assessment of vital status until 2 years after completion of SRT.

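### Patients removed under Section 5.2 without documented progression have no stated survival follow-up, so 2-year survival may be overstated

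*Combined protocol and SAP*

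**What the plan says.** Section 5.2 (Study Withdrawal) makes removal mandatory: "Patients must be removed from the study when any of the following occurs". The list covers withdrawn consent for treatment and procedures, loss to follow-up, study termination, and the investigator's opinion that "continuation of the study requirements would be harmful to the patient's well-being". Disease progression is not on the list, and nothing in 5.2 keeps vital status for a removed patient.

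Section 6.6 (Duration of Therapy) lists separately the reasons for ending study treatment, among them "Determination by the investigator that discontinuation is in the patient's best medical interest". It refers the reader to 5.2 but does not say when a patient leaves only treatment and when the patient leaves the study.

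Section 6.7.2 sets who is followed for response and survival, through 2 years after SRT: "Patients who remain on study will be assessed according to the study calendar". Table 5 has a survival follow-up row, and its footnote S reads: "For patients with post-SRT disease progression, follow-up can be limited to assessment of vital status until 2 years after completion of SRT".

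The outcomes concerned are endpoint 3.4.4, "Proportion of patients who are alive at 2 years after completion of SRT", and the Kaplan-Meier analysis of time to death in Section 13.4, where "Overall survival probabilities will be estimated with 95% confidence intervals at each follow-up time point during the 2-year follow-up". Section 13.4 uses all evaluable patients without saying which evaluable population. Section 13.5.2 replaces patients who have neither documented progression before week 24 nor a 24-week assessment.

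**The concern.** Vital status needs no visit or scan, so a patient can be too unwell for study procedures and still contribute to a survival endpoint. Read together, 5.2 and 6.7.2 end that contribution on removal. The patients affected are those the investigator thinks would be harmed by continuing, and it is plausible that they have a worse outlook than the rest.

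Kaplan-Meier estimation assumes that a censored patient has the same later survival as those still followed. If removal is linked to prognosis, that assumption fails and the curve sits too high. The simple proportion in 3.4.4 has the same weakness if patients of unknown status are left out. Two-year survival is a named secondary objective (2.2.4), and with about 42 patients a few unknown outcomes can move it by several percentage points.

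**Working it through.** The plan gives no 2-year survival rate, removal rate or survival precision, so there is no stated figure to reproduce. The check has two parts.

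**Part 1: which patients keep vital status as the text stands**

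| Patient | Governing text | Vital status to 2 years? |
|---|---|---|
| Stops treatment, stays on study | 6.6, 6.7.2 | Yes, by the calendar |
| Progresses after SRT, not removed | Footnote S | Yes |
| Removed under 5.2, no documented progression | 5.2, 6.7.2 | Not stated |

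The gap is the third row.

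**Part 2: what the gap could do to the estimate**

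Inputs: N = 42 evaluable patients (13.2). Assumed, because the documents are silent: a patients truly alive at 2 years, and k removed with unknown status.

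(a) *All k die and are excluded.* Truth = a/42; reading = a/(42 − k).

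| a (truth) | k = 2 | k = 4 | k = 8 |
|---|---|---|---|
| 13 (31.0%) | 13/40 = 32.5% | 13/38 = 34.2% | 13/34 = 38.2% |
| 17 (40.5%) | 17/40 = 42.5% | 17/38 = 44.7% | 17/34 = 50.0% |
| 21 (50.0%) | 21/40 = 52.5% | 21/38 = 55.3% | 21/34 = 61.8% |
| 25 (59.5%) | 25/40 = 62.5% | 25/38 = 65.8% | 25/34 = 73.5% |

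The overstatement runs from 32.5 − 31.0 = 1.5 points to 73.5 − 59.5 = 14.0 points.

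(b) *Removed patients die at the same rate as the rest.* With a = 21 and k = 4, two of the four are alive. Excluding them gives 19/38 = 50.0%, so there is no bias. Counting them as not alive gives 19/42 = 45.2%, an understatement.

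(c) *All k die and are counted as not alive.* The reading is 21/42 = 50.0%, with no bias.

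(d) *Kaplan-Meier instead of a proportion.* Take a = 21 and k = 4, all four dying unobserved, which leaves 21 − 4 = 17 observed deaths. Censoring at the start reproduces 21/38 = 55.3%. Suppose instead that 8 of the 17 deaths come first, then the four are censored, then the other 9 die. The number at risk falls from 34 to 30, and the estimate is (34/42) × (21/30) = 0.810 × 0.700 = 56.7%. The proportion in (a) therefore does not exaggerate what Kaplan-Meier would show in this example.

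(e) *Vital status kept.* The truth is observed and the bias is zero in every case.

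**The case against.** **A reader might infer that 5.2 and 6.6 attach different consequences to the same judgement.** The documents do not support that. Section 6.6 asks whether ending study treatment serves the patient; 5.2 asks whether the study requirements are harmful. Because 6.6 refers to 5.2, leaving treatment and leaving the study are already distinct. What stands is narrower: a frail patient could fall under either section, and the text does not say which applies.

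**A reader might infer that deteriorating patients in general lose vital status.** They do not. Progression is not a removal criterion, and patients who progress, the main deteriorating group, keep vital status under footnote S. That footnote permits lighter follow-up; it does not define who gets survival follow-up. The affected group may be small, and no passage suggests that such removals are common.

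**The direction of bias is assumed.** The table in (a) takes every removed patient to die. Working (b) and (c) show that the bias can be zero or negative, depending on mortality and counting. This stands.

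**Replacement under 13.5.2 may restore the denominator to 42.** If evaluable in 13.4 means efficacy-evaluable, a patient removed before week 24 without progression is replaced. This does not remove the problem. If replacements resemble the 38 who stayed, the expected number alive is 42 × 21/38 = 23.2, and 23.2/42 is again 55.3%. It does mean that collecting vital status alone is not enough: the survival population must also be defined.

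**Consent wording.** Consent pages are not in the material available, so no criticism of the consent options is made here.

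**Conclusion.** The concern holds in a limited form. As written, a patient removed under 5.2 without documented progression has no stated survival follow-up, and the plan has no rule for unknown vital status in 3.4.4 or 13.4. Two-year survival may be overstated if such removals carry a worse prognosis and are censored or excluded.

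The size cannot be derived from the documents. Under the assumption that 2 to 8 of 42 patients are removed, all die and all are dropped, the overstatement is 1.5 to 14.0 points for true survival of about 31% to 60%. With four removals and a true 50.0%, it is 5.3 points. These figures are illustrations at the unfavourable end, not predictions.

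A reader might go further and conclude that the survival result will be too high, or that the trial's conclusion is at risk. Neither follows. The direction depends on facts that the plan does not give, the endpoint is secondary, and the decision rule in 13.3 rests on disease control at 24 weeks. Nor do the documents say that survival will be compared with historical figures; 13.4 plans descriptive estimates with intervals.

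**What to change.** 1. In 5.2, 6.7.2 and footnote S, state that patients who are removed or stop visits for any reason other than withdrawal of consent for follow-up stay in vital-status follow-up, by records or telephone, to 2 years after SRT.
2. In 13.4, state that the survival analysis includes all patients who started SRT, that these patients stay in the denominator, and that they are censored only at last known vital status. Replacement under 13.5.2 then cannot drop them from survival. Say how any remaining unknown status is counted for the proportion in 3.4.4.
3. Ask the sponsor to reconcile 5.2 with 6.6 on when a patient leaves the study rather than only treatment. The clinical criterion itself is for the sponsor and investigators to set.

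The cost is minor wording changes and an occasional chart check or call at a centre that already collects vital status for patients who progress. The change is best made before further removals, because patients already removed may not have agreed to later contact.
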